#### 5.2. Determination of Sample Size

Patients will be randomized in a 1:1 ratio to double-blind LY900014 dosed 0 to 2 minutes before meals, or double-blind insulin lispro dosed 0 to 2 minutes before meals. Assuming a noninferiority margin (NIM) of 0.4%, no true difference between treatment arms, and a standard deviation (SD) of 1.1%, approximately 298 completers (149 in each treatment group) will provide 87% power to show noninferiority between LY900014 and insulin lispro in change from baseline to 26 weeks in hemoglobin A1c (HbA1c) using the upper limit of a 2-sided 95% confidence interval (CI; LY900014 – insulin lispro). Assuming a 15% dropout rate for 26 weeks, approximately 350 patients will need to be randomized.

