Safety Laboratory Tests (chemistry, hematology, lipids) – continuous analysis	All Patients in the Safety Population with a baseline and a postbaseline observation	Last of Visits 1-8	Visit 18 (planned) AND Last of Visits 9-18 (planned including early discontinuation visits), regardless of IP use
Safety Laboratory Tests (chemistry, hematology, lipids) – categorical analysis	All Patients in the Safety Population with a normal baseline (with respect to the direction being analyzed) and a postbaseline observation	Visits 1 -8 (including unplanned tests)	Visits 9-18 (including unplanned tests), regardless of IP use

Study	Patient Population	Baseline Observations	Postbaseline Observations
Period/Analysis			
TEAEs	All patients in the Safety Population	Prior to first dose of randomized IP (or Visit 8 date if missing) and after the first dose of open-label insulin lispro (or Visit 2 date if missing)	From first dose of randomized IP to last dose of randomized IP AND From first dose of randomized IP to Visit 801
Hypoglycemia events	All patients in the Safety Population	All Visits 2-8	All Visits 9-18 prior to discontinuation of IP
Weight and vital signs	All Patients in the Safety Population with a baseline and a postbaseline observation	Last of Visits 2-8	Visits 9-18 prior to discontinuation of IP AND Visits 9-801 regardless of IP use
Anti-insulin lispro antibody	Safety Population	Visit 2	Visits 3-801 regardless of IP use

Baseline and Postbaseline Definitions and Patient Po	pulation by Study	v Period and Type of Analysis
Buschne und i ostbuschne Demittons und i utent i	pullution by Stud	j i ci ioù una i jpe oi i inaijsis

Abbreviations: 1,5-AG = 1,5-Anhydroglucitol; ANCOVA = analysis of covariance; EQ-5D-5L = European Quality

of Life- 5 Dimensions 5 Level; EQ-VAS = EuroQol visual analogue scale; HbA1c = hemoglobin A1c; IP = investigational product; ITSQ = Insulin Treatment Satisfaction Questionnaire; ITT = intention-to-treat; LOCF = last-observation-carried forward; MMTT = mixed meal tolerance test; MMRM = mixed-effect model repeated measures; SMBG = self-monitored blood glucose; TEAE = treatment-emergent adverse event; WPAI-GH = Work Productivity and Activity Impairment General Health.

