#### 6.12.7.1. Treatment Emergent Anti-Insulin Lispro Antibody

The treatment-emergent anti-insulin lispro antibody (denoted as treatment-emergent antidrug antibody [TEADA] throughout this SAP) is based on the change from baseline (Visit 2) to postbaseline (post-Visit 2) in the anti-insulin lispro antibody level (percent binding). Treatment-emergent antidrug antibody can be sub-classified as either treatment-induced (not detected anti-insulin lispro antibody at baseline) or treatment-boosted (detected anti-insulin antibody at baseline):

The TEADA status during a specific analysis period will be determined using all data in the corresponding analysis period regardless of IP use. The summary for TEADA status and the anti-insulin lispro antibody level will use the same analysis data.

The number and percentage of patients with positive TEADA response during the analysis period of Visit 2 to Visit 801 will be summarized by treatment group. For patients with positive TEADA response anytime during the analysis period, the number and percentage of patients with positive

insulin cross-reactivity anytime during the analysis period, and the number and percentage of patients not meeting the TEADA criteria at Visit 801 will also be summarized by treatment group. Treatment groups will be compared by Fisher's exact test.

Both actual and change from baseline (Visit 2) for the anti-insulin lispro antibody level in percent binding will be summarized by scheduled visit prespecified in the protocol for patients with positive TEADA response from Visit 2 to Visit 801. The repeated measurement from Visit 2 to Visit 801 will be analyzed by an MMRM model with treatment, baseline value of the response variable, visit, and visit by treatment interaction as fixed factors and patient as the random factor. The ANCOVA model using treatment and baseline value as covariates will be used for the analysis of last non-missing observation prior to or at Visit 801 and the analysis of maximum percent binding during the analysis period of Visit 2 to Visit 801. Plot of anti-insulin lispro antibody percent binding will be generated based on the MMRM and the ANCOVA models.

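### Insulin cross-reactivity is compared, and antibody level summarized, only in TEADA-positive patients, and the population for the antibody-level models is not settled

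*SAP*

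**What the plan says.** SAP Section 6.12.7.1 bases TEADA status on the change in percent binding between Visit 2 and later visits, using all data regardless of IP use. Three layers of analysis follow.

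- **Incidence.** The number and percentage of TEADA-positive patients from Visit 2 to Visit 801 are given by arm, without restriction.
- **Cross-reactivity.** The denominator changes: "For patients with positive TEADA response anytime during the analysis period, the number and percentage of patients with positive" insulin cross-reactivity are reported by arm, as is the number no longer meeting the TEADA criteria at Visit 801. The paragraph ends with Fisher's exact test between arms.
- **Level.** Actual and change values of percent binding are "summarized by scheduled visit prespecified in the protocol for patients with positive TEADA response from Visit 2 to Visit 801". An MMRM, an ANCOVA of the last value and an ANCOVA of the maximum value come next, with no population named.

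Table 6.2 lists the Safety Population for anti-insulin lispro antibody, with baseline at Visit 2 and post-baseline "Visits 3-801 regardless of IP use". SAP Section 6.1 makes the Safety Population the default for safety analyses, and Section 6.12 refers to Tables 6.1 and 6.2 for the population. A listing of level and cross-reactivity covers the Safety Population, without a test. Protocol Section 10.3.4 leaves immunogenicity analyses to the SAP.

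**The concern.** TEADA status is an outcome, defined by the same assay value whose level is then summarized. If LY900014 raises percent binding, more LY900014 patients cross the cut-off. The added patients tend to lie close to it and draw down the mean of the LY900014 positives. Cross-reactivity has the same problem: if treatment raises the number of positives and the cross-reactive share among them stays the same, the conditional percentages agree although more LY900014 patients carry cross-reacting antibody.

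The selection is only partly post-randomization. Antibody is also sampled at Visit 8 (Protocol Section 2), after eight weeks of open-label lispro, so some patients can be TEADA-positive before taking randomized IP. Because the window runs to Visit 801, treatment can still alter membership, and the two positive groups are not comparable by design.

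What is at stake is a non-significant p-value read as no difference in antibody level or cross-reactivity when the choice of population made that result likely.

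**Working it through.** **Arm size.** The documents give no figure for the antibody analyses, so only the arm size is taken from SAP Section 5.2. That section's power figure reproduces: with margin 0.4, SD 1.1 and 149 per arm, SE = 1.1 × √(2/149) = 0.127, and power = Φ(0.4/0.127 − 1.96) ≈ 0.88, against the stated 87%. Completers divided by one minus dropout give 298/0.85 = 351, against about 350 randomized, or about 175 per arm.

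**Assumptions.** TEADA rate, cut-off, SD of percent binding and cross-reactive share are not in the documents. The figures below vary the TEADA rate and the shift, and use a normal change with SD 1.

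**Level, single measurement.** With control rate p₀, the cut-off is c = Φ⁻¹(1 − p₀). The mean among positives in an arm with shift μ is m(μ) = μ + φ(c − μ)/[1 − Φ(c − μ)]. The share of a shift δ that stays visible is [m(δ) − m(0)]/δ.

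Example with p₀ = 20% and δ = 0.3: c = 0.842, m(0) = 1.400, m(0.3) = 0.3 + 1.172 = 1.472. The difference is 0.072 SD, and 0.072/0.3 = 24%.

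| TEADA-positive on lispro | Visible, shift 0.3 SD | Visible, shift 0.5 SD |
|---|---|---|
| 20% | 24.0% | 25.5% |
| 30% | 29.0% | 30.9% |
| 40% | 34.2% | 36.4% |
| 70% | 53.5% | 56.4% |

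**Level, repeated samples.** A simulation used six post-Visit-2 samples (Visit 8 without effect, then Visits 10, 11, 15, 18 and 801), a shift of 0.5 SD and within-patient correlation 0.5-0.9. Patients counted as positive if any change exceeded the cut-off.

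| TEADA-positive on lispro | Visible, maximum value | Visible, last value |
|---|---|---|
| 10% | 18-21% | 28-46% |
| 20% | 25-26% | 33-50% |
| 30% | 30-32% | 38-52% |
| 50% | 42-43% | 48-59% |
| 70% | 56-57% | 60-68% |

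**Cross-reactivity, illustrative counts.** Suppose 35 lispro and 61 LY900014 patients are TEADA-positive out of 175 each, with about 60% cross-reactive in both arms, that is 21 and 37.

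| Comparison | Lispro | LY900014 | Fisher p |
|---|---|---|---|
| Cross-reactive among positives (as planned) | 21/35 = 60% | 37/61 = 61% | 1.0 |
| Cross-reactive among all patients | 21/175 = 12% | 37/175 = 21% | 0.03 |
| TEADA incidence (as planned) | 35/175 = 20% | 61/175 = 35% | 0.003 |

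**Population of the level models.** Read in order, the MMRM and ANCOVA sentences follow a sentence limited to TEADA-positive patients and appear to inherit that limit. Read against Section 6.1, Section 6.12 and Table 6.2, they use the Safety Population. Nothing in either document decides between the two readings.

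**The case against.** A reader might infer that the plan conceals most of any immunogenicity difference. The documents do not support that. The only stated immunogenicity endpoint (Protocol Table ITSD.1, SAP Table 4.1) is the incidence of treatment-emergent antibodies. It is summarized by arm in all patients and, on the natural reading, tested. In the illustration above that test gives p = 0.003. The number of cross-reactive patients per arm is also reported, so 21 against 37 would be seen in near-equal arms; what is missing is an all-patient test.

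Incidence does not replace the other analyses, however. At 20% positive on lispro, a 0.3 SD shift raises incidence to 1 − Φ(0.842 − 0.3) = 29.4%. Power at 175 per arm is then Φ[(0.094 − 1.96 × 0.0461)/0.0458] ≈ 53%, with pooled SE √(2 × 0.247 × 0.753/175) = 0.0461 and unpooled SE √[(0.160 + 0.208)/175] = 0.0458. Nor does incidence describe how high levels go or whether antibodies cross-react.

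It is also tempting to say that the level models are restricted to positives. That is an inference from sentence order, and the Safety Population default argues against it. This objection stands in part: for the models the finding is an unresolved conflict, not an established restriction. For the percent-binding summary and the cross-reactivity comparison the restriction is explicit.

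Finally, the size of the loss rests on assumed rates and a normal model, which fits poorly if many values are non-detected. That stands too, and is why ranges are given.

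**Conclusion.** The concern holds for cross-reactivity and for the percent-binding summary. Both are confined to a group defined by the assay and open to influence by randomized treatment, and both are pulled toward no difference. For the MMRM and ANCOVAs, the SAP must state which population applies; if it is the TEADA-positive group, the same weakness extends to them.

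The loss cannot be fixed from the documents. Under the single-measurement normal model with shifts of 0.3-0.5 SD, about 24-36% of a true level shift is visible at 20-40% positive on lispro. At 70% positive it is about 53-56%, so a general claim that most of the difference is lost would be wrong, and the simulated last value retains more than the maximum.

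The TEADA incidence comparison is unaffected, as are the primary and multiplicity-adjusted conclusions. The objective is exploratory, so severity is minor to moderate.

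**What to change.** In SAP Section 6.12.7.1:

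1. Compare between arms the proportion of patients who are both TEADA-positive and cross-reactive, with all Safety Population patients with antibody data as the denominator.
2. State that the percent-binding MMRM and both ANCOVAs use all Safety Population patients with a Visit 2 value and a post-baseline value. This also reconciles the section with Table 6.2.
3. Keep the TEADA-positive-only tables (cross-reactivity, status at Visit 801, percent binding by visit) as descriptive, without p-values.

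The cost is SAP wording and a changed population flag; the samples are already scheduled for all patients. The downside is that the level model will contain many non-detected values, so a rank-based check may be needed beside it.

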#### 6.11. Efficacy Analyses

#### 6.11.1. Primary Outcome and Methodology

The primary objective of this study (H1) is to test the hypothesis that LY900014 is noninferior to insulin lispro on glycemic control (NIM=0.4% for HbA1c) in patients with T1D, when administered as prandial insulin (0-2 minutes prior to the meal), in combination with basal insulin for 26 weeks.

The primary efficacy comparison will be based on the contrast between LY900014 and insulin lispro at Week 26 (Visit 18) from the MMRM analysis of change from baseline in HbA1c including data collected from all randomized patients prior to discontinuation of IP through Week 26. The model for the analysis of the primary efficacy endpoint of change from baseline in HbA1c will include the fixed class effects of treatment, strata (country, type of basal insulin, use of metformin at study entry), visit, and treatment-by-visit interaction, as well as the continuous, fixed covariates of baseline value. An unstructured covariance structure will be used to model the within-patient errors. Significance tests will be based on LS means and Type III tests. If this analysis fails to converge, the following covariance structures will be tested in order:

- Toeplitz with heterogeneity
- autoregressive with heterogeneity
- compound symmetry with heterogeneous variances
- Toeplitz
- autoregressive
- compound symmetry without heterogeneous variances

The first covariance structure that converges will be used. The Kenward-Roger approximation will be used to estimate denominator degrees of freedom.

LY900014 will be declared noninferior to insulin lispro if the upper limit of the 2-sided 95% CI for the LS mean difference in the change from baseline in HbA1c for LY900014 minus insulin lispro is below +0.4%.

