#### 6.12.7. Immunogenicity

Blood samples for immunogenicity testing will be collected to determine antibody production against insulin lispro for all enrolled patients since Visit 2 prior to the first dose of study-provided prandial insulin treatment. Therefore, the blood sample result at Visit 2 will be considered as the anti-insulin lispro level at baseline for this study.

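### The antibody-level models in SAP 6.12.7.1 count pre-randomization samples as outcomes, which dilutes the maximum-binding comparison, and their visit window contradicts Table 6.2

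*SAP*

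**What the plan says.** **Baseline.** SAP 6.12.7 states that "the blood sample result at Visit 2 will be considered as the anti-insulin lispro level at baseline for this study". The reason given is that this sample precedes the first prandial insulin supplied by the study.

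**MMRM.** SAP 6.12.7.1: "The repeated measurement from Visit 2 to Visit 801 will be analyzed by an MMRM model with treatment, baseline value of the response variable", followed by "visit, and visit by treatment interaction as fixed factors and patient as the random factor". No other covariance structure is named there. The unstructured choice ("An unstructured covariance structure will be used to model the within-patient errors") is written for HbA1c in section 6.11.1.

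**ANCOVA.** The same section plans ANCOVAs of the last non-missing value up to Visit 801 and "the analysis of maximum percent binding during the analysis period of Visit 2 to Visit 801", each adjusted for baseline.

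**Conflicting definitions.** The antibody row of Table 6.2 gives Visit 2 as baseline and "Visits 3-801 regardless of IP use" as postbaseline. Section 6.12.7.1 itself says that treatment-emergent antibody status (TEADA) "is based on the change from baseline (Visit 2) to postbaseline (post-Visit 2) in the anti-insulin lispro antibody level".

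**Population.** The by-visit level summary is "for patients with positive TEADA response from Visit 2 to Visit 801". The model sentences do not say whether that limit carries over.

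**Sampling.** The protocol's Schedule of Activities takes antibody samples at Visits 2, 8, 10, 11, 15, 18, 801 and early discontinuation. Its footnote on randomization places randomization after all Visit 8 procedures.

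**The concern.** Randomized treatment cannot affect a sample taken before randomization. Using such a sample as an outcome does harm in two ways.

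- **Maximum.** If a patient's peak is at Visit 2 or Visit 8, the outcome carries little or nothing of the treatment effect. The estimated difference moves toward zero, which is the wrong direction when looking for an immunogenicity signal with a new formulation. Table 6.2 removes Visit 2 but not Visit 8.
- **MMRM.** If Visit 2 is a response, it equals its own covariate, and its change from baseline is zero for every patient. A visit with almost no residual variance then enters the variance estimate used for every treatment contrast.

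The HbA1c row of Table 6.2 avoids the problem: its MMRM responses are Visits 11, 13, 15 and 18 only.

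The planned between-arm comparisons of antibody level are at stake. The TEADA incidence endpoint and the HbA1c analyses are not.

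**Working it through.** The SAP states no figure for these models, so there is none to reproduce. From the documents come the seven scheduled samples (Visits 2, 8, 10, 11, 15, 18, 801) and the two-sided 0.05 level (SAP 6.1). SDs, correlations, the treatment shift and the TEADA cut-off are assumed.

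**1. Maximum, all patients.** Suppose treatment adds a shift δ to every post-randomization sample. The maximum moves by δ when the peak is post-randomization and by less otherwise. To first order,

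share of δ recovered ≈ 1 − P(peak at Visit 2) − P(peak at Visit 8).

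Simulated with δ = 0.30 SD, 150 per arm, and correlation over 26 weeks as shown:

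| Setting | Peak at V2 | Peak at V8 | 1 − sum | Recovered, V2-801 | V8-801 | V10-801 |
|---|---|---|---|---|---|---|
| 0.5 | 16.2% | 7.5% | 76.3% | 77% | 90% | 101% |
| 0.7 | 15.2% | 7.2% | 77.6% | 78% | 89% | 99% |
| 0.9 | 12.0% | 7.4% | 80.6% | 82% | 91% | 100% |
| 0.7, with a 0.5 SD rise after Visit 2 | 3.2% | 10.1% | 86.7% | 88% | 90% | 100% |

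The approximation tracks the simulation. A separate run gave 0.23 as written, 0.26 without Visit 2 and 0.30 from Visit 10. Since 0.26/0.30 = 87%, the range on the Table 6.2 reading is about 87-91%.

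**2. Maximum, TEADA-positive patients only.** TEADA requires a later rise above Visit 2, so Visit 2 is never the peak and the V2-801 and V8-801 estimates are identical. Visit 8 is the peak in 2.5-9% of these patients. With assumed cut-offs of 0.5 or 1.0 SD, the V10-801 estimate is larger by 0.098/0.087 = 1.13 to 0.131/0.112 = 1.17, that is, 13-17%. This is the least stable figure here: it depends on the cut-off and on how closely Visit 8 follows Visit 2.

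**3. MMRM with Visit 2 as a response, patient as random factor.** Take SD 1 and constant correlation ρ, so that the random-intercept model is otherwise correct. The covariate is constant over visits, so the common slope is the average of the seven visit slopes: β = (1 + 6ρ)/7. The residual variance is (1 − β)² at Visit 2 and 1 − ρ² + (β − ρ)² at each other visit. The model's total variance is the average over the seven visits. The ratio of model SE to true SE is √(average/other-visit variance), and the test rejects with probability 2Φ(−1.96 × ratio).

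| ρ | β | Variance at V2 | Other visits | Average | SE ratio | Rejection rate |
|---|---|---|---|---|---|---|
| 0.5 | 0.571 | 0.184 | 0.755 | 0.674 | 0.944 | 6.4% |
| 0.7 | 0.743 | 0.066 | 0.512 | 0.448 | 0.936 | 6.7% |
| 0.9 | 0.914 | 0.007 | 0.190 | 0.164 | 0.929 | 6.9% |

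Simulation agrees: ratio 0.93-0.95 and rejection 6.2-7.3%. With responses from Visit 10 onward the ratio is 0.99-1.01 and rejection 4.6-5.5%. Dropping Visit 2 alone does as well in this case.

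**4. Same model, covariance misspecified.** With rising SDs or decaying correlation the ratio is 0.74-0.85 with Visit 2, 0.79-0.92 without it, and 0.84-0.95 from Visit 10. Much of that shortfall is therefore misspecification rather than Visit 2.

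**5. Unstructured covariance.** The Visit 2 residual variance is (1 − β)² times the Visit 2 variance and goes to zero as β approaches 1. With 120 patients, each tenfold reduction in 1 − β lowers −2 log L by 120 × 2 × ln 10 = 552.6. The profile shows this: −1239.7 at β = 0.9, −1792.4 at 0.99, −2345.0 at 0.999. The likelihood has no maximum. If the slope is fixed at 1, the SE relative to ANCOVA is √(2/(1 + ρ)): 1.155, 1.085 and 1.026 for ρ = 0.5, 0.7 and 0.9. That is 3-15% larger, not smaller.

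**The case against.** The strongest reply is that Visit 2 was never meant to be an outcome. SAP 6.1 names Table 6.2 as the place that fixes baseline and postbaseline observations. The antibody row starts at Visit 3, and section 6.12.7.1 itself treats postbaseline as after Visit 2. The disputed range may simply name the analysis period, as it does for TEADA incidence, where Visit 2 cannot be an outcome. This stands in part: the Visit 2 problem is an internal contradiction, not an established analysis choice. It does not touch Visit 8, which remains in the window on either reading.

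A reader might infer that the MMRM confidence intervals are too narrow as planned, and by more than 10%. The documents do not support that. It needs the literal Visit 2 reading together with the random-intercept model. The part due to Visit 2 is then about 5-7%, and larger shortfalls mix in covariance misspecification. Under an unstructured covariance the trouble is a failed fit, which would be noticed.

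A reader might also apply the all-patient dilution without qualification. The preceding sentence of the SAP may limit the models to TEADA-positive patients, where Visit 2 dilutes nothing.

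Three further replies are fair. Visit 8 in the MMRM does little harm, because the visit-by-treatment terms give it its own contrast. Adjusting for Visit 8 is a matter of precision, not a correction. And antibody level is not a listed endpoint: TEADA incidence is, at the tertiary/exploratory tier, without multiplicity control.

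**Conclusion.** The concern holds in a limited form. On either reading, the maximum-binding ANCOVA includes at least one sample that treatment cannot affect, and it is biased toward no difference. With all patients it recovers about 77-88% of a true shift as written and about 87-91% under Table 6.2. With TEADA-positive patients only, Visit 8 alone dilutes: the estimate from Visit 10 onward was 13-17% larger in the settings tried. The MMRM fault is conditional on Visit 2 being used as a response. It is then a standard error about 5-7% too small under the patient-random-factor model, or a degenerate fit under an unstructured one.

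The direction for the maximum follows from the design. The sizes rest on assumed SDs, correlations, a 0.30 SD shift, assumed TEADA cut-offs and no missing data, and are illustrative. The consequence is confined to exploratory comparisons of antibody level. TEADA incidence, the primary analysis and the sample size are unaffected.

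**What to change.** Amend SAP 6.12.7.1 and the antibody row of Table 6.2 so that they agree:

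- Keep Visit 2 as the baseline covariate and the TEADA reference only.
- Limit the MMRM responses to Visits 10, 11, 15, 18 and 801.
- Limit the maximum and the last non-missing observation to the same visits plus early-discontinuation samples taken after randomization. As worded, the last-observation analysis could use a pre-randomization value for a patient with no later sample. Early-discontinuation samples stay out of the MMRM unless a rule maps them to a visit.
- Show Visit 2 and Visit 8 levels descriptively.
- State the population (all safety patients or TEADA-positive only) and the covariance structure.

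Optionally, add Visit 8 percent binding as a second covariate. For the maximum, simulation put the gain at a standard error about 10-14% lower. Patients without a Visit 8 sample would need a rule, such as using their Visit 2 value.

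The cost is SAP wording before unblinding. No new data are needed.

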7.2.1.5. Transitioning off Study Insulin Therapy

Patients should take their last dose of study insulin (LY900014 or insulin lispro) at Visit 18 with the MMTT if performed the same date as Visit 18 or the evening the day prior to Visit 18 if the MMTT is performed prior to Visit 18 or at early discontinuation.

No special instructions for transition to nonstudy prandial insulin are necessary for patients who were using basal bolus therapy prior to study entry. After completion of study treatment, these patients will restart the prandial insulin therapy used prior to study entry or may transition to a rapid-acting insulin analog other than insulin lispro if the patient was treated with regular human insulin prestudy. Patients may remain on the basal insulin used during the study (if it was changed at Visit 2) at the discretion of the investigator or return to their prestudy basal insulin.

Patients who were using premixed insulins prior to study entry may choose to stay on basal bolus regimen at the discretion of the investigator. However, patients who were not on lispro product prior to entry should NOT use lispro product during the safety follow-up period.

Additional guidance for insulin therapy after the treatment period is provided in Section 7.8.2.

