A listing of anti-insulin lispro antibody at each visit will be provided. The listing will include antiinsulin lispro antibody status (detected/not detected), anti-insulin lispro antibody percent binding, TEADA status (positive/negative), insulin cross-reactivity status, insulin cross-reactivity percent binding for the safety population.

Subgroup analysis for the following selected efficacy and safety variables will be performed by the TEADA status during the treatment period of Visit2 to Visit 801:

- Use data prior to discontinuation of IP:
  - HbA1c and change from baseline in HbA1c
  - 1-hour and 2-hour PPG excursions
  - o basal, prandial, and total insulin dose
  - event rate (per patient per year) of overall hypoglycemic events
- Use all data regardless of IP use:
  - o treatment-emergent injection site reaction and hypersensitivity reaction

The analyses for HbA1c and change from baseline in HbA1c will be performed using an MMRM model for the primary analysis and the HbA1c data prior to discontinuation of IP. The model will include additional fixed terms of subgroup, subgroup by treatment interaction, subgroup by visit interaction, and 3-way interaction of treatment, subgroup, and visit.

The PPG excursions will be analyzed by the ANCOVA model same as the model specified in Section 6.11.2. with data collected before permanent discontinuation of IP. The model will include additional terms of subgroup, subgroup by treatment interaction, subgroup by visit interaction, and 3-way interaction of treatment, subgroup, and visit.

The subgroup analysis for insulin dose will use the MMRM model specified in Section 6.11.5 using data collected before permanent discontinuation of IP. The model will include additional fixed terms of subgroup, subgroup by treatment interaction, subgroup by visit interaction, and 3-way interaction of treatment, subgroup and visit.

The treatment emergent injection site reaction and hypersensitivity reaction will be analyzed by a logistic regression model including terms of treatment, subgroup, and treatment by subgroup interaction. All data regardless of IP use will be used for this analysis.

The negative binomial regression model specified in Table 6.5 with additional terms of subgroup, treatment by subgroup interaction will be used for the subgroup analysis of overall hypoglycemia event rate while on IP.

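### Antibody samples taken after study insulin has stopped can decide a patient's TEADA subgroup for four outcomes that use on-treatment data only

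*SAP*

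**What the plan says.** **How status is set.** SAP 6.12.7.1 says that TEADA status in a given period "will be determined using all data in the corresponding analysis period regardless of IP use". The subgroup analysis "will be performed by the TEADA status during the treatment period of Visit2 to Visit 801". SAP Table 6.2 agrees: the antibody baseline is Visit 2 and the postbaseline window is "Visits 3-801 regardless of IP use".

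**What is split by that status.** The same section lists two sets of outcomes.
- HbA1c, 1-hour and 2-hour PPG excursions, insulin doses and the overall hypoglycemia rate carry the instruction "Use data prior to discontinuation of IP".
- For injection-site and hypersensitivity reactions, "All data regardless of IP use will be used for this analysis".

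**Timing.** Study insulin ends at Week 26 (protocol Figure ITSD.1, footnote d), and Visit 801 follows four weeks after Visit 18 (protocol 5.3.1). Patients who stop IP early but stay in the study complete the remaining visits, including Visit 801. They have no further mixed-meal test (protocol 8.1 and 9.1.4.3).

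**The concern.** For the first set of outcomes, the window that defines the subgroup runs past the window that supplies the data. A patient who is negative through Visit 18 and first positive at Visit 801 joins the TEADA-positive group for outcomes that were complete four weeks earlier. For a patient who stopped IP early and stayed in follow-up, the gap can be much longer.

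The analysis asks whether the difference between arms depends on antibody status. Adding patients whose antibodies were first found after the outcome dilutes the TEADA-positive group and pulls the interaction toward zero. In an immunogenicity assessment, no interaction is the reassuring answer, so the error runs in the less cautious direction.

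**Working it through.** **Step 1. Compare the windows.**

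| Item | Start | End |
|---|---|---|
| TEADA status | after Visit 2 (Week -8) | Visit 801 (Week 30), on or off IP |
| HbA1c, PPG, dose, hypoglycemia | randomization (Week 0) | end of IP, at latest Week 26 |

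The status window spans 8 + 26 + 4 = 38 weeks, of which the last 4 follow the latest possible outcome.

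**Step 2. Check whether an earlier cut is possible.** The Schedule of Activities has antibody samples at Visits 2, 8, 10, 11, 15, 18 and 801 and at early discontinuation. Status through Visit 18 can be derived from data already planned. SAP 6.1 counts laboratory data as on IP up to 14 days after the last dose. A Visit 801 sample taken four weeks (28 days) after a Visit 18 last dose falls outside that limit.

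**Step 3. See which outcomes are affected.** A completer first positive at Visit 801 can affect all four. An early stopper can affect HbA1c, dose and hypoglycemia but not PPG. The PPG analysis needs an on-IP Visit 18 test (SAP Table 6.2), which that patient does not have.

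**Step 4. Dilution.** Neither document gives a figure for this analysis, so there is none to reproduce. Let p be the share of patients positive by Week 26 (by the end of IP, for early stoppers) and q the share first positive only afterwards. Suppose true positives differ from negatives by Δ and late positives do not differ from negatives. The observed contrast is then

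(p × Δ + q × 0)/(p + q) = Δ × p/(p + q).

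The documents state neither p nor q. Over assumed ranges, the share of Δ that is kept is:

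| p | q = 1% | q = 3% | q = 5% |
|---|---|---|---|
| 10% | 91% | 77% | 67% |
| 20% | 95% | 87% | 80% |
| 30% | 97% | 91% | 86% |
| 40% | 98% | 93% | 89% |

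Of 298 completers, q of 1% to 5% is about 3 to 15 patients.

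**Step 5. Effect on the interaction test (HbA1c).** The SD of 1.1% and the 298 completers come from protocol 10.1. With the 0.4% margin they give 88.1% power for noninferiority by the normal approximation and 87.9% by noncentral t, consistent with the stated 87%. The test level is 0.10, unadjusted (SAP 6.12.7.1), taken here as two-sided. Assume a true interaction of 0.4%, p = 20%, q = 3% and even allocation within subgroups. With P the share classed positive,

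SE = 1.1 × √(4/(298P) + 4/(298(1 − P))).

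- Status cut at Week 26: P = 0.20, SE = 0.319. Power = Φ(0.4/0.319 − 1.645) ≈ 35%.
- Status to Visit 801: P = 0.23, SE = 0.303, effect = 0.4 × 0.870 = 0.348. Power = Φ(0.348/0.303 − 1.645) ≈ 31%.

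**The case against.** Five points can be made for the plan.

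1. **No late positive has been shown.** Neither document gives a TEADA incidence or a rate of first positivity at Visit 801, and the numerical TEADA criteria cannot be seen in the public text. This stands: patients can be misclassed, but the documents do not show that any will be. A reader might spread first positives evenly over the sampling window and read off a misclassified share. Nothing in the documents supports that, particularly as lispro exposure changes after Week 26.

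2. **First detection at Visit 801 does not prove that the antibody arose after Week 26.** This also stands. The p/(p+q) result assumes that late positives have no antibody effect; if some do, the dilution is smaller.

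3. **The interaction test is weak either way,** as Step 5 shows. That limits the gain, but it does not justify using samples taken after the outcome.

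4. **An earlier cut does not settle timing completely.** A patient first positive at Visit 18 would still count as positive for hypoglycemia in earlier weeks, and positives from the open-label lead-in still count. Early stoppers would also have fewer samples in which to turn positive. These limits remain after the fix, but none of them requires samples taken after the outcome is complete.

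5. **The Visit 801 summary is a separate matter.** A reader might infer that the count of "patients not meeting the TEADA criteria at Visit 801 will also be summarized by treatment group" is flawed because follow-up is not a uniform washout. Among prior basal-bolus users, "these patients will restart the prandial insulin therapy used prior to study entry", which may be lispro, whereas "patients who were not on lispro product prior to entry should NOT use lispro product during the safety follow-up period". The SAP plans only a descriptive count by arm and does not say that it measures resolution once lispro stops. Splitting it by lispro use would be a reporting preference, not a correction.

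**Conclusion.** The concern holds as a mismatch of windows in four subgroup analyses: HbA1c, PPG excursions, insulin dose and overall hypoglycemia rate. Followed as written, the SAP can class a patient by a sample taken after the outcome is complete. For PPG this can happen only through Visit 801 in patients who complete treatment.

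On the assumed ranges the contrast keeps between two thirds and nearly all of its size, and in the worked example power falls by about 4 points. Both results rest on assumed rates and on late positives having no antibody effect.

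The point is minor. A reader might infer that the efficacy conclusions are at risk, but these are unadjusted subgroup tests and do not enter the primary or multiplicity-adjusted tests. The injection-site and hypersensitivity analyses use all data regardless of IP use, so the same mismatch does not arise there. TEADA is a post-randomization factor that treatment may influence, so even with the window corrected the comparison is not a causal one.

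**What to change.** In SAP 6.12.7.1:

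- For the four on-IP outcomes, define TEADA status from post-Visit 2 samples up to Visit 18 (or the early discontinuation visit) taken no later than 14 days after the last IP dose. This is the SAP 6.1 rule for laboratory data.
- Keep the Visit 2 to Visit 801 window for the TEADA incidence summary and for injection-site and hypersensitivity reactions.
- Stop calling Visit 2 to Visit 801 the treatment period. SAP 6.1 uses that term for randomization to Week 26 before IP discontinuation and lists the period to Visit 801 separately.

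The cost is one extra derived status variable from samples already scheduled, with no new visits and no change in sample size. The downside is slightly fewer TEADA-positive patients in these subgroups.
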